3.2 Rationale for study design

This extension study offers the opportunity to Japanese patients who completed Epoch 4 of the CACZ885N2301 study to be treated with ACZ885 until approval of the drug is granted in Japan or the development of the drug is suspended in Periodic Fever Syndromes. Therefore, an open

label design has been selected. The visit schedule follows on from the Epoch 4 of CACZ885N2301 study.

3.3 Rationale for dose/regimen, route of administration and duration of treatment

Since this is an extension study of the CACZ885N2301 study, patients will receive the study drug with a starting dose based on final dose regimen received in the CACZ885N2301 study. Study duration will continue until approval of the drug is granted in Japan or the development of the drug is suspended in Periodic Fever Syndromes.

3.4 Rationale for choice of comparator

Not applicable.

3.5 Purpose and timing of interim analyses/design adaptations

Not applicable.

3.6 Risks and benefits

In TRAPS, HIDS/MKD and FMF, antipyretics, such as NSAIDs and paracetamol, often have some effect at reducing fever and associated symptoms, but they do not prevent or change the course of flare ([Ter Haar et al 2013](#), [Hoffman and Simon 2009](#)). Regular, repeated dosing is often required for the duration of the episode, which raises concern for the occurrence of adverse effects, including gastrointestinal irritation or liver toxicity.

For the past 30 years, maintenance-dose colchicine has been the mainstay of therapy for preventing attacks and substantially reducing the risk of amyloidosis in patients with FMF. Occasionally, compliance can be affected by the gastrointestinal adverse effects that are sometimes associated with increasing the colchicine dose. There are rare patients (in the range of 5-10%) with FMF who are considered to be colchicine resistant (incomplete response to adequate colchicine dosing). However, colchicine is less effective in TRAPS and HIDS/MKD.

Corticosteroids have limited clinical efficacy in most of the recurrent febrile syndromes, with reports of very high doses being required to achieve any benefit.

Thus the risks are associated with the use of high doses of antipyretics, colchicine and corticosteroids, which offer only symptomatic relief, without sustained benefit.

Preliminary data from the 4 small pilot studies with canakinumab in these 3 indications both in adult and pediatric patients, as well as the ongoing worldwide pharmacovigilance activities have not identified any new safety signals specific for patients with TRAPS, HIDS/MKD, crFMF in patients treated with canakinumab.

The risk to subjects in this trial will be minimized by compliance with the inclusion/ exclusion criteria, close clinical and laboratory monitoring, adherence to the protocol guidelines for dose administration/escape treatment rules and implementation of a Risk Management Plan in place for canakinumab.

Canakinumab is known to be highly effective and safe in children and adults with CAPS, a spectrum of inherited auto-inflammatory syndromes that are similar to TRAPS, HIDS/MKD

and crFMF. Preliminary data from the 4 PoC open-label trials with canakinumab in these 3 indications in both in adult and pediatric patients has shown canakinumab to be effective, and potentially able to treat the underlying inflammation, rather than just the disease symptoms. And the result from the CACZ885N2301 study Epoch 2 data, which is placebo-controlled Phase 3 confirmatory study with canakinumab in these 3 indications, has shown the overall favorable benefit-risk profile.

4 Population

This study population will be Japanese patients who completed Epoch 4 of the CACZ885N2301 study.

4.1 Inclusion criteria

Patients eligible for inclusion in this study must fulfill all of the following criteria:

1. Completed Epoch 4 of the CACZ885N2301 study in Japan before the approval of canakinumab in Japan.
2. Before or at Visit 1, written informed consent must be obtained before any assessment is performed from those ≥ 20 years of age. Parent or legal guardian's written informed consent and child's assent, if appropriate, are required before any assessment is performed for patients < 20 years of age.

4.2 Exclusion criteria

Patients fulfilling any of the following criteria are not eligible for inclusion in this study. No additional exclusions may be applied by the investigator, in order to ensure that the study population will be representative of all eligible patients/subjects.

1. Any conditions or significant medical problems in which the investigator judges the patient should not enter this extension study.
2. Pregnant or nursing (lactating) women
3. Female adolescents (≤ 18 years of age) of childbearing potential who do not agree to abstinence or, if sexually active, do not agree to the use of contraception as defined in the exclusion criterion for women of child bearing potential. For further information, please refer to [Section 6.5.3](#).
4. Women of child-bearing potential, defined as all women physiologically capable of becoming pregnant, unless they are using effective methods of contraception during dosing of study treatment. Effective contraception methods include:
 - a. Total abstinence (when this is in line with the preferred and usual lifestyle of the subject. Periodic abstinence (e.g., calendar, ovulation, symptothermal, post-ovulation methods) and withdrawal are not acceptable methods of contraception
 - b. Female sterilization (have had surgical bilateral oophorectomy with or without hysterectomy) or tubal ligation at least six weeks before taking study treatment. In case of oophorectomy alone, only when the reproductive status of the woman has been confirmed by follow up hormone level assessment
 - c. Male sterilization (at least 6 m prior to screening). For female subjects on the study, the vasectomized male partner should be the sole partner for that subject

- d. Barrier methods of contraception: Condom or Occlusive cap (diaphragm or cervical/vault caps) with spermicidal foam/gel/film/cream/ vaginal suppository
- e. Use of oral, injected or implanted hormonal methods of contraception or other forms of hormonal contraception that have comparable efficacy (failure rate < 1%), for example hormone vaginal ring or transdermal hormone contraception
- f. Placement of an intrauterine device (IUD) or intrauterine system (IUS)
In case of use of oral contraception women should have been stable on the same pill for a minimum of 3 months before taking study treatment.
Women are considered post-menopausal and not of child bearing potential if they have had 12 months of natural (spontaneous) amenorrhea with an appropriate clinical profile (e.g. age appropriate, history of vasomotor symptoms) or have had surgical bilateral oophorectomy (with or without hysterectomy) or tubal ligation at least six weeks ago. In the case of oophorectomy alone, only when the reproductive status of the woman has been confirmed by follow up hormone level assessment is she considered not of child bearing potential.

5 Treatment

5.1 Study treatment

5.1.1 Investigational and control drugs

Novartis will provide the following investigational treatment:

- Canakinumab solution for injection in vial which contains 150 mg canakinumab in 1 mL solution

5.1.2 Additional treatment

No additional treatment beyond investigational drug and control drug are included in this trial.

5.2 Treatment arms

Patients will continue the study drug based on final dose regimen received (e.g. one of the following regimen) in the CACZ885N2301 study.

- ACZ885 150 mg (or 2 mg/kg for patients weighing ≤ 40 kg) q4w
- ACZ885 150 mg (or 2 mg/kg for patients weighing ≤ 40 kg) q8w
- ACZ885 300 mg (or 4 mg/kg for patients weighing ≤ 40 kg) q4w
- ACZ885 300 mg (or 4 mg/kg for patients weighing ≤ 40 kg) q8w

5.3 Treatment assignment and randomization

This is an open label study.

5.4 Treatment blinding

Not applicable.

5.5 Treating the patient

Sponsor qualified medical personnel will be readily available to advise on trial related medical questions or problems.

5.5.1 Patient numbering

Patient numbers used in the preceding CACZ885N2301 study will be used continuously for those patients enrolling in this extension study.

5.5.2 Dispensing the study drug

Each study site will be supplied with study drug.

5.5.3 Handling of study and additional treatment

5.5.3.1 Handling of study treatment

Study treatment must be received by a designated person at the study site, handled and stored safely and properly, and kept in a secured location to which only the investigator and designees

have access. Upon receipt, all study treatment must be stored according to the instructions specified on the labels. Clinical supplies are to be dispensed only in accordance with the protocol. Technical complaints are to be reported to the respective Novartis CPO Quality Assurance.

Medication labels will be in the local language and comply with the legal requirements of each country. They will include storage conditions and Lot number for the study treatment but no information about the patient.

The investigator must maintain an accurate record of the shipment and dispensing of study treatment in a drug accountability log. Monitoring of drug accountability will be performed by monitors during site visits or remotely and at the completion of the trial. Patients will be asked to return all unused study treatment and packaging at the end of the study or at the time of discontinuation of study treatment.

At the conclusion of the study, and as appropriate during the course of the study, the investigator will return all unused study treatment, packaging, drug labels, and a copy of the completed drug accountability log to the Novartis monitor or to the Novartis address provided in the investigator folder at each site.

5.5.3.2 Handling of additional treatment

Not applicable.

5.5.4 Instructions for prescribing and taking study treatment

The s.c. injections of investigational treatment may be administered into the patient's arm or thigh. Detailed instructions on the preparation and administration of the study drugs will be described in the Pharmacist Manual provided in the CACZ885N2301 study.

All patients will receive 1 or 2 s.c. injections every 4 or 8 weeks based on the final dose regimen received in the CACZ885N2301 study and depending upon criteria met for up-titration ([Section 3.1.2](#)) until TD/ PSW.

All dosages prescribed and dispensed to the patient and all dose changes during the study must be recorded on the Dosage Administration Record CRF.

5.5.5 Permitted dose adjustments and interruptions of study treatment

Investigational treatment dose adjustments and/or interruptions other than those detailed in [Section 3.1.2](#) are not permitted.

All dose changes must be recorded on the Dosage Administration Record CRF.

5.5.6 Rescue medication

Standard doses of NSAIDs and corticosteroids can be used as needed basis to treat the signs and symptoms of TRAPS, HIDS/MKD or crFMF during acute flares at the discretion of the investigator.

Use of rescue medication must be recorded on the concomitant medications page in the CRF.

5.5.7 Concomitant medication

The investigator must instruct the patient to notify the study site about any new medications he/she takes after the patient was enrolled into the study. All medications, procedures and significant non-drug therapies (including physical therapy and blood transfusions) administered after the patient is enrolled into this extension study must be recorded in the concomitant medications / significant non-drug therapies eCRF.

Each concomitant drug must be individually assessed against all prohibited medication. If in doubt the investigator should contact the Novartis medical monitor before allowing a new medication to be started.

5.5.8 Prohibited medication

Use of the treatments displayed in [Table 5-1](#) is NOT allowed after Screening. Once canakinumab is approved for Periodic Fever Syndromes (TRAPS, HIDS/MKD, or crFMF), it can be used according to the package insert.

Table 5-1 Prohibited treatment

Medication	Action to be taken
Anakinra	Investigational treatment to be discontinued ²
Riloncept, tocilizumab, rituximab and any other biologics ¹ (investigational or marketed)	Investigational treatment to be discontinued ²
Etanercept, adalimumab, infliximab, or any TNF inhibitor (investigational or marketed)	Investigational treatment to be discontinued ²
Leflunomide, thalidomide, cyclosporine, or i.v. Ig	Investigational treatment to be discontinued ²
Tofacitinib	Investigational treatment to be discontinued ²
6-Merceptopurine, azathioprine, cyclophosphamide, or chlorambucil	Investigational treatment to be discontinued ²
Any other investigational non-biological drug	Investigational treatment to be discontinued ²
Any live vaccination ¹	Investigational treatment to be discontinued ²
Treatment for tuberculosis	Investigational treatment to be discontinued

¹ It is recommended not to initiate any live vaccination or biologic treatment until 3 months after the last dose of investigational treatment. Killed or inactivated vaccines may be permitted according to the investigator's discretion.

² Investigational treatments must be permanently discontinued but patient will remain in the study and will be followed-up for safety.

5.5.9 Emergency breaking of assigned treatment code

This is an open label study.

5.6 Study completion and discontinuation

5.6.1 Study completion and post-study treatment

A patient will be considered to have completed the study when the patient has completed the last visit of extension- treatment epoch planned in the protocol.

For all patients a safety follow-up visit should be conducted (e.g. by telephone) 30 days after last visit 199 or TD/PSW, or 8 weeks after last injection of investigational drug, whichever is later. The investigator must provide follow-up medical care for all patients who are prematurely withdrawn from the study, or must refer them for appropriate ongoing care. This care does not require any special treatment but it is recommended not to initiate any live vaccination or biologic treatment until 3 months after the last dose of study treatment.

5.6.2 Discontinuation of study treatment

Discontinuation of study treatment for a patient occurs when study drug is stopped earlier than the protocol planned duration, and can be initiated by either the patient or the investigator.

The investigator must discontinue study treatment for a given patient if, on balance, he/she believes that continuation would negatively impact the risk/benefit of trial participation.

Study treatment must be discontinued under the following circumstances:

- Emergence of the following adverse events:
 - a. Absolute QTcF > 500 msec, confirmed by repeat electrocardiogram (ECG) measurements
 - b. Serious infections combined with neutropenia Common Toxicity Criteria (CTC) grades ≥ 1 (ANC < $2.0 \times 10^9/L$)
 - c. CKD as per NKF stages ≥ 4 : eGFR ≤ 29 mL/min/1.73 m²
 - d. Confirmed diagnosis of latent or active Tuberculosis
 - e. Onset of any malignancy
- Any of the following laboratory abnormalities:
 - a. Neutropenia CTC Grades ≥ 2 : ANC < $1.5 \times 10^9/L$
 - b. Thrombocytopenia CTC Grade 4: Platelets < $10.0 \times 10^9/L$
- Pregnancy
- Use of prohibited treatment as per [Table 5-1](#)
- Any other protocol deviation that results in a significant risk to the patient's safety

If discontinuation of study treatment occurs, the patient should NOT be considered withdrawn from the study. The patient should return to the clinic as soon as possible, after discontinuation of study drug, for a study treatment discontinuation visit. Treatment discontinuation visit assessments detailed in the "treatment discontinuation visit" in [Table 6-1](#) should be completed and recorded in the eCRF. The investigator must determine the primary reason for the patient's premature discontinuation of study treatment and record this information on the Dosage Administration eCRF.

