6.5.2 Laboratory evaluations

All laboratory evaluations will be conducted locally. Clinically notable laboratory findings are defined in [Appendix 1](#).

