8. Creatinine clearance (CrCl) (Cockcroft-Gault formula) ²: $\geq 25\%$ decrease from baseline
9. Triglycerides: > 5 x ULN

Hematology

1. Hemoglobin: ≥ 20 g/L decrease from baseline or < 100 g/L
2. Platelet count ³
 - a. CTC Grade 1: $< \text{Lower Limit of Normal (LLN)} - 75 \times 10^9/\text{L}$
 - b. CTC Grade 2: $< 75 - 50 \times 10^9/\text{L}$
 - c. CTC Grade 3: $< 50 - 25 \times 10^9/\text{L}$
 - d. CTC Grade 4: $< 25 \times 10^9/\text{L}$
3. White blood cell count ³
 - a. CTC Grade 1: $< \text{LLN} - 3 \times 10^9/\text{L}$
 - b. CTC Grade 2: $< 3 - 2 \times 10^9/\text{L}$
 - c. CTC Grade 3: $< 2 - 1 \times 10^9/\text{L}$
 - d. CTC Grade 4: $< 1 \times 10^9/\text{L}$
4. Absolute neutrophils ³
 - a. CTC Grade 1: $< \text{LLN} - 1.5 \times 10^9/\text{L}$
 - b. CTC Grade 2: $< 1.5 - 1 \times 10^9/\text{L}$
 - c. CTC Grade 3: $< 1 - 0.5 \times 10^9/\text{L}$
 - d. CTC Grade 4: $< 0.5 \times 10^9/\text{L}$
5. Absolute lymphocytes: $< \text{LLN}$
6. Absolute eosinophils: ≥ 2.5 x, ≥ 3 x ULN

Urinalysis

- a. Protein urine dipstick: $\geq ++$

Notable laboratory abnormalities in pediatric patients (< 18 years of age)

Post-baseline values in pediatric patients (at the time of the assessment) will be flagged as notable abnormalities as follows:

Biochemistry

1. ALT (SGPT): > 3 x, 5 x, 10 x, and 20 x Upper Limit of Normal (ULN) ¹
2. AST (SGOT): > 3 x, 5 x, 10 x, and 20 x ULN ¹
3. Elevation of AST and/ or ALT (> 3 x ULN) accompanied by elevated bilirubin (> 1.5 x ULN, > 2 x ULN) ¹
4. Any elevations of bilirubin; elevated total bilirubin (TBL) to > 2 x ULN ¹
5. Any elevations of ALP > 1.5 x ULN ¹
6. GGT: \geq 3 x, 5 x ULN
7. Creatinine (serum): \geq 1.5 x ULN
8. Creatinine clearance (Schwartz formula ⁴): \geq 25% decrease from baseline, \geq 2 consecutive visits
9. Total Cholesterol: \geq 1.5 x ULN
10. Triglycerides: \geq 5.7 mmol/L
11. Creatinine clearance (Schwartz formula ⁴): \geq 25% decrease from baseline for \geq 3 months in duration in combination with protein urine dipstick resulting in new protein \geq 1+, \geq 3 months in duration

Hematology

1. Hemoglobin: \geq 20 g/L decrease from baseline or < 85 g/L (patients < 16 years of age) or < 100 g/L (patients \geq 16 years of age)
2. Platelet count ³
 - e. CTC Grade 1: < Lower Limit of Normal (LLN) – 75 x 10⁹/L
 - f. CTC Grade 2: < 75 – 50 x 10⁹/L
 - g. CTC Grade 3: < 50 – 25 x 10⁹/L
 - h. CTC Grade 4: < 25 x 10⁹/L
3. White blood cell count ³
 - e. CTC Grade 1: < LLN – 3 x 10⁹/L

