 - f. CTC Grade 2: < 3 – 2 x 10⁹/L
 - g. CTC Grade 3: < 2 – 1 x 10⁹/L
 - h. CTC Grade 4: < 1 x 10⁹/L
4. Absolute neutrophils ³
 - e. CTC Grade 1: < LLN – 1.5 x 10⁹/L
 - f. CTC Grade 2: < 1.5 – 1 x 10⁹/L
 - g. CTC Grade 3: < 1 – 0.5 x 10⁹/L
 - h. CTC Grade 4: < 0.5 x 10⁹/L
5. Absolute lymphocytes: < LLN
6. Absolute Eosinophils: \geq 1.1 x ULN, \geq 0.45 x 10⁹/L

Urinalysis

- Protein urine dipstick: $\geq +$ for ≥ 3 months in duration

¹ Adapted from FDA Guidance for Industry Drug-Induced Liver Injury: Premarketing Clinical Evaluation (July 2009)

² Cockcroft-Gault formula (Men): $\text{CrCl (mL/min)} = [((140 - \text{age (years)}) \times \text{weight (kg)}) / (\text{serum creatinine } (\mu\text{mol/L}) / 88.4) (\text{mg/dL}) \times 72]$

² Cockcroft-Gault formula (Women): $\text{CrCl (mL/min)} = [((140 - \text{age (years)}) \times \text{weight (kg)}) / (\text{serum creatinine } (\mu\text{mol/L}) / 88.4) (\text{mg/dL}) \times 72] \times 0.85$

³ Common Terminology Criteria for Adverse Events, US Department of Health and Human Services (v4.03: 14-Jun-2010)

⁴ Creatinine clearance was derived using the following formula:

$\text{CrCl (mL/min/1.73 m}^2) = [0.413 \times \text{length (cm)} / (\text{serum creatinine mg/dl})]$ (Schwartz et al 2009).

14 Appendix 2: Liver event and Laboratory trigger Definitions and Follow-up Requirements

Table 14-1 Liver Event and Laboratory Trigger Definitions

	Definition/ threshold
LIVER LABORATORY TRIGGERS	$3 \times \text{ULN} < \text{ALT} / \text{AST} \leq 5 \times \text{ULN}$ $1.5 \times \text{ULN} < \text{TBL} \leq 2 \times \text{ULN}$
LIVER EVENTS	ALT or AST $> 5 \times \text{ULN}$ ALP $> 2 \times \text{ULN}$ (in the absence of known bone pathology) TBL $> 2 \times \text{ULN}$ (in the absence of known Gilbert syndrome) ALT or AST $> 3 \times \text{ULN}$ and INR > 1.5 Potential Hy's Law cases (defined as ALT or AST $> 3 \times \text{ULN}$ and TBL $> 2 \times \text{ULN}$ [mainly conjugated fraction] without notable increase in ALP to $> 2 \times \text{ULN}$) Any clinical event of jaundice (or equivalent term) ALT or AST $> 3 \times \text{ULN}$ accompanied by (general) malaise, fatigue, abdominal pain, nausea, or vomiting, or rash with eosinophilia Any adverse event potentially indicative of a liver toxicity*

*These events cover the following: hepatic failure, fibrosis and cirrhosis, and other liver damage-related conditions; the non-infectious hepatitis; the benign, malignant and unspecified liver neoplasms

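### The stop for serious infection with neutropenia gives a CTC grade and an ANC cut-off that agree only where the local lower limit of normal is 2.0 × 10⁹/L

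*Protocol*

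**What the plan says.** Protocol section 5.6.2 lists the circumstances in which study treatment must be discontinued. Item (b) under adverse events is "Serious infections combined with neutropenia Common Toxicity Criteria (CTC) grades" of 1 or more, followed in brackets by ANC < 2.0 × 10⁹/L. Further down, among the laboratory abnormalities, neutropenia of Grade 2 or more, printed as ANC < 1.5 × 10⁹/L, is a stop in its own right, with or without infection.

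Protocol Appendix 1 grades "Absolute neutrophils" separately. Its pediatric list gives "CTC Grade 1: < LLN – 1.5 x 10⁹/L" and its adult list gives the same limits; Grade 2 starts below 1.5 × 10⁹/L in both. SAP section 5.3.1 repeats these grades for adults and children. Both documents attribute the grading to "Common Terminology Criteria for Adverse Events, US Department of Health and Human Services (v4.03: 14-Jun-2010"). Section 5.6.2 names no CTC version and does not refer to Appendix 1.

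On whose limits apply, Protocol section 6.5.2 says "All laboratory evaluations will be conducted locally", and SAP section 2.8.3 agrees. Neither document gives a value for the ANC LLN.

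**The concern.** One mandatory stopping criterion is expressed in two ways that are not equivalent under the protocol's own grading scale. The grade is tied to a laboratory-dependent limit; the bracketed number is fixed. No section says that the number overrides the grade or the reverse, so two sites, or a site and a monitor, could reach different answers on whether a patient with a serious infection had to stop.

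This matters because safety and tolerability is the only objective (Protocol section 2.1), and discontinuation as the glossary defines it is permanent. Relevant protocol deviations also have to be determined before database lock (Protocol section 8.3). In the disputed range, whether failure to stop was a deviation depends on which half of the criterion is read.

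**Working it through.** No sample-size or power formula applies. The check compares thresholds, all in units of 10⁹/L.

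**Inputs from the documents**
- Number reading of item (b): ANC < 2.0 (Protocol section 5.6.2).
- Grade reading of item (b): Grade 1 or worse. Grade 1 is below LLN down to 1.5, and Grade 2 starts below 1.5 (Protocol Appendix 1; SAP section 5.3.1).
- Stand-alone stop: ANC < 1.5 (Protocol section 5.6.2).

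**Input that is assumed**
- Local ANC LLN: not given, so varied from 1.5 to 2.5.

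**Step 1. Do the printed cut-offs follow from Appendix 1?** For Grade 2 or more, section 5.6.2 prints < 1.5 and Appendix 1 starts Grade 2 below 1.5, so they match. For Grade 1 or more, section 5.6.2 prints < 2.0 and Appendix 1 gives < LLN. These match only if LLN = 2.0.

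**Step 2. Where can the two readings differ?** Below 1.5 both are met, and the stand-alone stop applies in any case. So only ANC of 1.5 or above matters. There the number reading is ANC < 2.0 and the grade reading is ANC < LLN.
- If LLN < 2.0, the number alone is met from max(LLN, 1.5) to below 2.0. The width is 2.0 − max(LLN, 1.5).
- If LLN > 2.0, the grade alone is met from 2.0 to below LLN. The width is LLN − 2.0.

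**Step 3. Numbers put in**

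| Assumed LLN | Number only | Grade only | Width |
|---|---|---|---|
| 1.5 | 1.5 to < 2.0 | none | 2.0 − 1.5 = 0.5 |
| 1.6 | 1.6 to < 2.0 | none | 2.0 − 1.6 = 0.4 |
| 1.8 | 1.8 to < 2.0 | none | 2.0 − 1.8 = 0.2 |
| 2.0 | none | none | 0 |
| 2.2 | none | 2.0 to < 2.2 | 2.2 − 2.0 = 0.2 |
| 2.5 | none | 2.0 to < 2.5 | 2.5 − 2.0 = 0.5 |

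At an assumed LLN of 1.5 the grade reading adds nothing to the stand-alone stop. At any one laboratory the disagreement runs in one direction only, fixed by the side of 2.0 on which its LLN falls.

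**The case against.** The strongest reply is that the rule can be carried out as printed. The number stands on the same line as the grade, section 5.6.2 does not cite Appendix 1, and Appendix 1 serves to flag notable values, not to trigger stopping. A site would probably apply 2.0. That is a fair account of likely practice, and it makes this largely a labelling inconsistency. It does not remove the conflict: the protocol never says that the number governs, the grade is stated first, and section 7.1 sends investigators to Appendix 1 for laboratory alert ranges.

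Several stronger inferences should be resisted.

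- A reader might infer that adherence to the stop could not be checked, because the SAP flags contain no 2.0 cut-off. The documents do not support this. Laboratory values are listed by patient (Protocol section 9.5.2.4; SAP section 2.8.3), neutrophils are in the panel, and SAEs are listed. Each ANC can be read against 2.0 directly.
- A reader might infer that one discordant case would alter the tolerability results. Only listings are produced, with no statistical summary (Protocol section 9; SAP section 2.1), so no estimate would move and the case would appear individually under either reading.
- A reader might infer that a patient who fails one reading stays on drug. Section 5.6.2 also obliges the investigator to stop when continuing would worsen the risk/benefit balance, so that does not follow.
- A reader might turn the band widths into a ratio of one reading's reach to the other's. That would only restate the assumed LLNs; it measures neither patients nor risk.

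**Conclusion.** The inconsistency stands and is worth correcting, but it is small. As written, the infection-plus-neutropenia stop has two criteria that agree only where the local LLN is 2.0 × 10⁹/L. Elsewhere, an infected patient with ANC between 2.0 and the local LLN (or 1.5, where the LLN is lower than that) meets one and not the other.

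Across assumed LLNs of 1.5 to 2.5 the disputed band is at most 0.5 × 10⁹/L wide. Its size and direction at any site rest wholly on an LLN that the documents do not supply. A case also needs a serious infection and an ANC in that band together, among at most 10 patients (Protocol section 9.8). The documents give no basis for estimating how often that would occur; few if any patients are likely to be affected.

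**What to change.** Reconcile item (b) of Protocol section 5.6.2 with Appendix 1 and SAP section 5.3.1, so that the stop rests on one stated criterion: either the grade or a fixed ANC, with the other removed or expressly made subordinate. The choice of limit belongs to the sponsor's clinical team.

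This is best done in the same amendment as the platelet line of that list, where section 5.6.2 prints thrombocytopenia Grade 4 as < 10.0 × 10⁹/L and Appendix 1 and the SAP print < 25 × 10⁹/L. Correcting the platelet line alone would leave the neutrophil conflict in place.

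The cost is one line of a protocol amendment and no new data. If a fixed ANC is kept, a matching flag in SAP section 5.3.1 would be a convenience only, since ANC values are already listed by patient.

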5.3 Laboratory parameters derivations

5.3.1 Clinically notable laboratory values

Notable laboratory abnormalities in adult patients (≥ 18 years of age)

Post-baseline values will be flagged as notable abnormalities as follows:

Biochemistry

1. ALT (SGPT): > 3 x, 5 x, 10 x, and 20 x Upper Limit of Normal (ULN) ¹
2. AST (SGOT): > 3 x, 5 x, 10 x, and 20 x ULN ¹
3. Elevation of AST and/ or ALT (> 3 x ULN) accompanied by elevated bilirubin (> 1.5 x ULN, > 2 x ULN) ¹
4. Any elevations of bilirubin; elevated total bilirubin (TBL) to > 2 x ULN ¹
5. Any elevations of ALP > 1.5 x ULN ¹
6. Gamma-Glutamyltransferase (GGT): > 3 x ULN

7. Creatinine (serum): $\geq 3 \times \text{ULN}$
8. Creatinine clearance (CrCl) (Cockcroft-Gault formula) ²: $\geq 25\%$ decrease from baseline
9. Triglycerides: $> 5 \times \text{ULN}$

Hematology

1. Hemoglobin: $\geq 20 \text{ g/L}$ decrease from baseline or $< 100 \text{ g/L}$
2. Platelet count ³
 - CTC Grade 1: $< \text{Lower Limit of Normal (LLN)} - 75 \times 10^9/\text{L}$
 - CTC Grade 2: $< 75 - 50 \times 10^9/\text{L}$
 - CTC Grade 3: $< 50 - 25 \times 10^9/\text{L}$
 - CTC Grade 4: $< 25 \times 10^9/\text{L}$
3. White blood cell count ³
 - CTC Grade 1: $< \text{LLN} - 3 \times 10^9/\text{L}$
 - CTC Grade 2: $< 3 - 2 \times 10^9/\text{L}$
 - CTC Grade 3: $< 2 - 1 \times 10^9/\text{L}$
 - CTC Grade 4: $< 1 \times 10^9/\text{L}$
4. Absolute neutrophils ³
 - CTC Grade 1: $< \text{LLN} - 1.5 \times 10^9/\text{L}$
 - CTC Grade 2: $< 1.5 - 1 \times 10^9/\text{L}$
 - CTC Grade 3: $< 1 - 0.5 \times 10^9/\text{L}$
 - CTC Grade 4: $< 0.5 \times 10^9/\text{L}$
5. Absolute lymphocytes: $< \text{LLN}$
6. Absolute eosinophils: $\geq 2.5 \times, \geq 3 \times \text{ULN}$

Urinalysis

Protein urine dipstick: $\geq ++$

Notable laboratory abnormalities in pediatric patients (< 18 years of age)

Post-baseline values in pediatric patients (at the time of the assessment) will be flagged as notable abnormalities as follows:

Biochemistry

1. ALT (SGPT): > 3 x, 5 x, 10 x, and 20 x Upper Limit of Normal (ULN) ¹
2. AST (SGOT): > 3 x, 5 x, 10 x, and 20 x ULN ¹
3. Elevation of AST and/ or ALT (> 3 x ULN) accompanied by elevated bilirubin (> 1.5 x ULN, > 2 x ULN) ¹
4. Any elevations of bilirubin; elevated total bilirubin (TBL) to > 2 x ULN ¹
5. Any elevations of ALP > 1.5 x ULN ¹
6. GGT: ≥ 3 x, 5 x ULN
7. Creatinine (serum): ≥ 1.5 x ULN
8. Creatinine clearance (Schwartz formula ⁴): ≥ 25% decrease from baseline, ≥ 2 consecutive visits

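### The mandatory platelet stop in Protocol 5.6.2 is labelled CTC Grade 4 but set at <10 ×10⁹/L, while Appendix 1 and SAP 5.3.1 put Grade 4 at <25; a lesser conflict concerns treatment interruptions

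*Protocol*

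**What the plan says.** **Platelet stop.** Protocol 5.6.2 lists circumstances in which study treatment has to be discontinued. One of the two laboratory items is "Thrombocytopenia CTC Grade 4: Platelets < $10.0 \times 10^9/L". The section names no CTC version and does not refer to Appendix 1.

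**Platelet grades.** Protocol Appendix 1 grades platelets separately for adults ("d. CTC Grade 4: $< 25 \times 10^9/\text{L") and for patients under 18 ("h. CTC Grade 4: < 25 x 10⁹/L"). SAP 5.3.1 repeats both lists, with the adult entry reading "CTC Grade 4: $< 25 \times 10^9/\text{L" and the pediatric entry giving the same limit. Each document footnotes its lists to CTCAE v4.03.

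**Interruptions.** Protocol 5.5.5 permits no dose adjustment or interruption beyond what 3.1.2 sets out, and 3.1.2 describes only stepwise up-titration after a flare. Elsewhere the protocol does contemplate interruption:

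- Section 7.1 includes interrupting treatment, and reducing the dose, among the ways an adverse event may be handled.
- Table 14-2 tells the investigator to consider interruption for an adverse event suggesting liver toxicity.
- Table 15-1 does so for a creatinine rise of at least 50% and for new proteinuria. Section 7.4 sends sites to that table.

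**The concern.** A mandatory stopping rule should have one reading. Here an investigator who works from the grade and one who works from the number reach different answers for the same platelet count, and a monitor could not say which of them had deviated. Safety and tolerability is the only objective, and section 8.4 provides no data monitoring committee that might notice uneven application. Patients on the 4-weekly regimen are also dosed between the 8-weekly scheduled visits at which Table 6-1 places hematology, so a result read one way rather than the other can be followed by further doses.

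The interruption conflict is of a different kind. An investigator who pauses treatment because an appendix or section 7.1 points that way breaches 5.5.5 by doing so.

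**Working it through.** No power, alpha or effect size is involved: the study produces listings only. The check compares thresholds.

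**Step 1. Platelet limit attached to Grade 4 (×10⁹/L)**

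| Place | Function | Grade 4 limit |
|---|---|---|
| Protocol 5.6.2 | Mandatory stop | <10 |
| Protocol Appendix 1, adult | Flag for notable values | <25 |
| Protocol Appendix 1, pediatric | Flag for notable values | <25 |
| SAP 5.3.1, adult | Flag for notable values | <25 |
| SAP 5.3.1, pediatric | Flag for notable values | <25 |

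All 4 grading lists agree on <25. The 5.6.2 figure does not reproduce from its own label on the only platelet scale the documents contain.

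**Step 2. Does 5.6.2 otherwise use that scale?** The other laboratory item in 5.6.2 is neutropenia of Grade 2 or more, set at ANC <1.5 ×10⁹/L. Appendix 1 starts neutrophil Grade 2 at <1.5. Label and number match, so a reader would expect the platelet item beside it to follow the same scale.

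**Step 3. Where the two readings part**

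- If the label governs, stop when platelets <25.
- If the number governs, stop when platelets <10.
- They disagree for 10 ≤ platelets < 25, a band of 25 − 10 = 15 ×10⁹/L.

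Example: a count of 15 is Grade 4 in Appendix 1 and in the SAP listing, since Grade 3 ends at 25. The label requires a stop. Because 15 is not below 10, the number does not. Counts below 10 stop under both readings, and counts of 25 or more under neither.

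**Step 4. Patients affected.** Section 9.8 caps enrolment at 10. The documents give no frequency for counts in the band, so no expected number can be calculated.

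**Step 5. Interruptions**

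| Place | Interruption contemplated? | Discontinuation also offered? |
|---|---|---|
| 5.5.5 through 3.1.2 | No (up-titration only) | Not addressed |
| 7.1, handling of adverse events | Yes | Yes (withdrawal) |
| Table 14-2, possible liver toxicity | Yes, to be considered | Yes |
| Table 15-1, creatinine rise ≥50% | Yes, to be considered | No |
| Table 15-1, new proteinuria | Yes, to be considered | Yes |

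Three table rows (1 + 2) and section 7.1 contemplate a step that 5.5.5 does not allow. In two of the three rows the investigator can stay within 5.5.5 by discontinuing. Only the creatinine row names interruption with no discontinuation beside it.

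**The case against.** **The number is the rule.** Section 5.6.2 prints its own limit and does not cite Appendix 1, which only flags values. On this view there is one rule, <10, with a loose label. It stands that Appendix 1 is not a stopping rule and that nothing shows a split between sites to be likely. But the label is part of the criterion, and the documents define it nowhere else. Either reading leaves something in 5.6.2 to correct.

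**The number may be deliberate.** A reader might infer that <10 is a proven error. The documents do not support that: 5.6.2 names no CTC version and may follow another. They establish a mismatch, not which side of it is wrong, and the threshold is a clinical decision.

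**The patient is protected anyway.** A reader might infer that patients with counts of 10 to <25 must be kept on drug. They need not be. Section 5.6.2 separately obliges the investigator to stop when risk/benefit is unfavourable, and Appendix 1 flags such a count. This stands and limits the harm. It does not settle whether the stop is compulsory.

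**The neutropenia label might look wrong too.** The serious-infection item reads "Serious infections combined with neutropenia Common Toxicity Criteria (CTC) grades ≥ 1 (ANC < $2.0 \times 10^9/L", while Appendix 1 starts Grade 1 at the laboratory's lower limit of normal. These differ only if that limit is not 2.0. Laboratories are local and the documents give no limit, so a conflict appears only under an assumed value. It is not part of this point.

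**Interruptions.** A reader might infer that 5.5.5 prevents a pause needed for safety. It does not: the table rows ask only for consideration, and section 11.1 expects immediate safety action even where it deviates from the protocol. What stands is that such a pause counts as a deviation.

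**Conclusion.** The platelet criterion in 5.6.2 is inconsistent as written. Its Grade 4 label means <25 ×10⁹/L on the only platelet scale in the documents, and its number is <10. The consequence is confined to counts from 10 to <25 in a study of at most 10 patients, and to whether the stop there is mandatory or left to judgment. This rests on reading the label through CTCAE v4.03, the version cited in Appendix 1 and the SAP. If 5.6.2 was written to another version, the mismatch within the protocol remains but the number may be the intended one.

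The interruption conflict is real but smaller, and amounts to how a safety pause is classified.

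Neither point affects an estimate or a listing. SAP 5.3.1 applies <25 to the notable-value listing whichever stop is chosen. The platelet item should be fixed because it is a mandatory safety threshold and the correction is cheap.

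**What to change.** **5.6.2.** Set the platelet stop at <25 ×10⁹/L and name CTCAE v4.03, so that label and number agree with Appendix 1 and the SAP. The price is a somewhat earlier mandatory stop for a patient with a count from 10 to <25. If the sponsor confirms that <10 is intended, keep the number and delete the Grade 4 label.

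**5.5.5.** Add an exception for safety interruptions under section 7.1 and Appendices 2 and 3, recorded on the Dosage Administration Record CRF. An exception limited to the appendices would still conflict with 7.1. Because 7.1 also mentions dose reduction, the same sentence should say whether that is allowed.

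**Cost.** One protocol wording amendment, covering one item in 5.6.2 and one sentence in 5.5.5, with the approvals that section 11.1 requires. No SAP change and no additional patients, visits or tests.
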